5. Patient affiliated with a social security system

Exclusion criteria:

1. Minors, pregnant or breastfeeding women
2. Obstetric procedures
3. Surgeries under Local Anesthesia (LA) or peripheral nerve block
4. Procedures performed outside an interventional room (e.g., operating theater or interventional radiology)
5. Procedures related to previous surgical complications
6. Patients reoperated during follow-up (no double inclusion for the second surgery)
7. Organ transplantation
8. Patients already intubated preoperatively
9. Outpatient surgery
10. Refusal to participate or inability to provide informed consent
11. Persons deprived of liberty or adults under guardianship
12. Participation in another interventional study.

Primary endpoint:

Occurrence of acute respiratory failure (ARF) within 7 postoperative days during hospitalization, validated by the blinded adjudication committee with respect to the randomization arm.

Secondary endpoints:

Assessment of the safety and tolerability of the strategy under study:

- Discomfort or intolerance to NIV, defined as the inability to achieve the target of 6 to 8 hours per day due to premature termination of sessions caused by intolerance, despite proper implementation of NIV, including excessive leaks when these are the reason for stopping sessions
- Skin lesions at contact points between the interface and the patient's skin
- Anastomotic suture dehiscence (digestive or bronchial) when caused by a total pressure (PEEP + IPAP) > 20 cmH₂O
- Gastric distension defined as aeric distension of the gastric air pocket evidenced by imaging or gastric tube aspiration
- Occurrence of aspiration of secretions or vomit whose evacuation was hindered by the NIV mask

Any ARF must lead to investigation of its etiology using appropriate examinations:

Infectious pneumonia defined by a Modified Clinical Pulmonary Infection Score (CPIS) > 6, with microbiological thresholds of culture concentrations >10³ CFU/ml for a protected distal sample, >10⁴ CFU/ml for bronchoalveolar lavage, and >10⁶ CFU/ml for tracheal aspiration

The Modified Clinical Pulmonary Infection Score (modified CPIS)

CPIS Points	0	1	2
Tracheal secretions	Rare	Abundant	Abundant + purulent
Chest X-ray infiltrates	No infiltrate	Diffused	Localized
Temperature, °C	≥36.5 and ≤38.4	≥38.5. and ≤38.9	≥39 or ≤36.4
Leukocytes count, per mm ³	≥4,000 and ≤11,000	<4,000 or >11,000	<4,000 or >11,000 + band forms ≥500

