
- Death from any cause during hospitalization for surgery

Assessment of an effect on patient reintubation:

- Reintubation due to respiratory failure (ARF)
- Reintubation due to non-respiratory failure, excluding reintubations specifically for a new surgical or interventional radiology procedure
- Time to reintubation to assess delayed reintubation (characterized by a non-significant difference in reintubation rate between groups but a longer delay in the NIV group)

Assessment of an effect on length of stay in ICU and duration of invasive or non-invasive mechanical ventilation:

- Number of days of invasive mechanical ventilation (intubated or tracheostomized) during hospitalization for surgery, including episodes of reintubation
- Number of days of non-invasive mechanical ventilation (NIV) during hospitalization for surgery, including prophylactic and therapeutic NIV.

**Assessment of an effect on the incidence of healthcare-associated infections, defined according to
Centers for Disease Control (CDC) criteria:**

- Infectious pneumonia: see secondary endpoint criteria
- Urinary tract infection: fever $> 38^{\circ}\text{C}$ and urine culture showing no more than two microbial species, at least one with a concentration $> 10^5 \text{ CFU/ml}$, in a patient with no other obvious source of infection
- Catheter-related infection: fever $> 38^{\circ}\text{C}$, positive catheter culture or sample, and resolution of fever within 48 hours after catheter removal without antibiotic change and no other identified source of infection
- Bacteremia: fever $> 38^{\circ}\text{C}$ and at least one positive blood culture (two or more if coagulase-negative staphylococcus)
- Surgical site infection

Data collection is performed prospectively throughout the first 7 days of hospitalization for surgery.

D) Description of Investigational Medicinal Products

MEDICAMENTS :

Name of the Medicinal Product (INN)	Brand Name	Pharmaceutical Form	Route of Administration	Dosage per Administration
Medical Liquid Oxygen	N/A	Gas	N/A	

Therapeutic regimen:

The ventilatory mode used will be an assisted mode (PSV or BiPAP), as these have shown a stronger (86) and more sustained effect (29) than CPAP alone.

The interface—nasal mask, face mask, or helmet—is chosen according to the unit's usual practice.

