Study of Associations (Qualitative and/or Quantitative Variables):

For each parameter of interest, a bivariate analysis will be performed, possibly complemented by a multivariate analysis adapted to the outcome variable to explore potential associations.

For bivariate analyses, the use of parametric or non-parametric tests will depend on sample size and/or variable distribution. The significance threshold is set at 0.05, and all tests will be two-sided.

The statistical test used will be Pearson's Chi-square test (or Fisher's exact test) for qualitative variables. For quantitative variables, the statistical tests used will be ANOVA or the non-parametric Kruskal-Wallis test.

The association between each presumed risk factor and the parameter of interest will be estimated using the relative risk (RR) and its 95% confidence interval.

A multivariate logistic regression analysis will estimate the adjusted RR and its 95% confidence interval for each retained factor (conservative threshold of 0.20 in univariate analysis).

Early Mortality:

Overall survival is defined as the time between the date of operating room discharge and the date of death if the patient dies within 7 days, or the end of study follow-up at Day 7. The Kaplan-Meier method will be used to estimate survival rates and plot survival curves. The Log-Rank test will be used to compare survival curves. Event-free survival is defined as the time between operating room discharge and the date of occurrence of the event (PPC) or the date of last follow-up if censored.

A semi-parametric Cox proportional hazards regression model will estimate for each variable the crude association (Hazard Ratio, HR) between the factor studied and death (bivariate analysis), then the adjusted HR in multivariate analysis.

The significance threshold for including other variables in the multivariate analysis will be 0.20. If several candidate variables are redundant, the most representative variable will be retained for the model.

Subgroup Analyses (Exploratory):

Subgroup analyses will address the occurrence of endpoints:

- According to patient characteristics at inclusion (medical history, ARISCAT score components, type of surgery, and planned anesthetic technique).
- The subgroup of patients receiving NIV as curative (under conditions noted at session start) will be compared to the group receiving NIV only prophylactically in terms of outcome at Day 7.

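### Event-free survival has PPC as its only named event, so, read literally, a death without PPC is censored and never counts as a failure

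*Combined protocol and SAP*

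**What the plan says.** Section E, Early Mortality, defines two time-to-event measures.

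- **Overall survival:** "Overall survival is defined as the time between the date of operating room discharge and the date of death if the patient dies within 7" (the unit is days). A patient still alive is followed to "the end of study follow-up at Day 7". Death is the event and the end point of follow-up is explicit.
- **Event-free survival:** "Event-free survival is defined as the time between operating room discharge and the date of occurrence of the event (PPC"). The alternative ending reads "or the date of last follow-up if censored". Death is not mentioned, and last follow-up is not tied to a day.

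Between the two definitions stand the methods: "The Kaplan-Meier method will be used to estimate survival rates and plot survival curves" and "The Log-Rank test will be used to compare survival curves". The Cox model that follows is for death. Cumulative incidence and competing risks are not mentioned anywhere.

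Elsewhere, the primary endpoint in section C is "Occurrence of acute respiratory failure (ARF) within 7 postoperative days during hospitalization", confirmed by a blinded adjudication committee. The secondary endpoints include "Death from any cause during hospitalization for surgery". Section C also says that data are collected prospectively over the first 7 days of the surgical stay, and section F gives a 7-day follow-up period.

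**The concern.** Readers take a measure called event-free survival to mean alive without the event. As defined, it has two endings, PPC or censoring, so a patient who dies without a PPC can only be censored. This has two consequences.

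1. Kaplan-Meier treats censoring as uninformative: it assumes that censored patients would have gone on to have PPCs at the rate of those still observed. A patient who has died cannot have a PPC, so the estimated PPC probability is too high.
2. The deaths are missing from the curve. If deaths without PPC differed between arms, this curve and its log-rank test would hardly show it.

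The sentence also leaves open what last follow-up means for a patient discharged alive before Day 7, and it names PPC where the primary endpoint is ARF.

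**Working it through.** The plan states no figure for event-free survival, so there is none to reproduce. The check is a reading of the definition followed by an illustration of size.

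**Reading.** Death ends overall survival as an event. In event-free survival the only event is PPC and the only alternative is censoring. A death without PPC is not the event, so it falls under censoring.

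**Inputs**
- PPC incidence by Day 7, *p*: 30% and 15%. These are the ARF rates for standard care and prophylactic non-invasive ventilation (NIV) in the sample-size justification, used as stand-ins because no PPC rate is given for the two arms.
- Death without PPC by Day 7, *q*: not given. Assumed at 1%, 2%, 5% and 10%.
- Arm size: 266/2 = 133.
- Constant cause-specific hazards over 7 days (assumption).

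**Formulas.** The total cumulative hazard is −ln(1 − p − q), of which PPC has the share p/(p + q). Hence
- one minus Kaplan-Meier with deaths censored = 1 − (1 − p − q)^(p/(p+q));
- PPC or death = p + q.

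Example with p = 0.30, q = 0.10: 1 − 0.60^0.75 = 0.318, against a true PPC incidence of 0.300 and a composite of 0.400.

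| True PPC | Death without PPC | Such deaths per 133 | 1 − KM, deaths censored | Overstatement (points) | PPC or death |
|---|---|---|---|---|---|
| 30% | 1% | 1.3 | 30.17% | 0.17 | 31% |
| 30% | 2% | 2.7 | 30.34% | 0.34 | 32% |
| 30% | 5% | 6.7 | 30.87% | 0.87 | 35% |
| 30% | 10% | 13.3 | 31.83% | 1.83 | 40% |
| 15% | 1% | 1.3 | 15.08% | 0.08 | 16% |
| 15% | 2% | 2.7 | 15.16% | 0.16 | 17% |
| 15% | 5% | 6.7 | 15.41% | 0.41 | 20% |
| 15% | 10% | 13.3 | 15.85% | 0.85 | 25% |

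The overstatement is small. The larger gap is between the curve and the proportion a reader would expect it to show, alive without PPC.

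**Unequal deaths.** Control: p = 30%, q = 2%. NIV: p = 15%, with q varied. The PPC-only hazard ratio is the ratio of the PPC cumulative hazards; the composite hazard ratio is the ratio of the total cumulative hazards.

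| NIV death without PPC | PPC-only HR | Composite HR |
|---|---|---|
| 2% | 0.455 | 0.483 |
| 5% | 0.463 | 0.579 |
| 10% | 0.477 | 0.746 |

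The PPC-only ratio barely moves while the composite does. The last row needs an assumed imbalance of 10% against 2%.

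**Discharge, under one reading only.** If last follow-up meant discharge, and 30% of patients (assumed) left event-free before Day 7, the same formula without deaths gives 1 − 0.40^(1/2) = 36.8% for an in-hospital 30%, and 1 − 0.55^(1/3) = 18.1% for 15%. If last follow-up means Day 7, this difference does not arise.

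**The case against.** The best defence is that little depends on this sentence. Event-free survival is not a listed primary or secondary endpoint and is not among the secondary comparisons in section E. The same subsection analyses death by Kaplan-Meier, log-rank and Cox, and all-cause in-hospital death is a secondary endpoint. A log-rank test with deaths censored is also a legitimate cause-specific comparison. All of this stands and limits the importance of the point. It does not make the label right.

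A reader might also infer more than the text supports:

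- *That the plan says deaths are censored.* It never says who is censored. This follows from the two endings given, and the use of Kaplan-Meier for this measure is likewise inferred from its place in the subsection.
- *That a dead patient is kept at risk.* A censored patient leaves the risk set; the fault is the assumption about later risk.
- *That discharged patients are censored at discharge.* The data-collection sentence in section C allows this, but the Day 7 end of follow-up in section E and the 7-day period in section F allow the other reading. The text is ambiguous.
- *That death handling explains any mismatch with the primary result.* The primary endpoint is adjudicated ARF and this measure uses PPC, so the two would differ anyway.
- *That excess deaths would go unseen in the trial.* They would be nearly invisible only on this curve.
- *That each such death biases Kaplan-Meier by 1/133 = 0.75 point.* That is the shift from counting the death in a composite. The Kaplan-Meier overstatement is much smaller, as the table shows.

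**Conclusion.** The definition is wrong as written for a measure called event-free survival: taken literally, death without PPC never counts as a failure. With death without PPC assumed at 1% to 10% and constant hazards, one minus Kaplan-Meier overstates a 30% PPC incidence by about 0.2 to 1.8 points, and the curve omits 1 to 10 points of deaths. Both ranges rest on a death rate that the documents do not give, and on ARF rates standing in for PPC. The consequence is modest, since the measure is not a listed endpoint and mortality has its own analysis. The correction is still worth making, because a published curve with this label would be read as alive without complication. The meaning of last follow-up and the choice between PPC and ARF are open points in the same sentence, not demonstrated errors of analysis.

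**What to change.** Amend the event-free survival sentence in section E, choosing one of two forms:

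1. Keep the name, and run the clock from leaving the operating room to whichever comes first, PPC or death from any cause, with administrative censoring at Day 7.
2. Rename it time to PPC, and report cumulative incidence by arm with death without PPC as a competing event.

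In either form, state that a patient discharged alive before Day 7 without an event stays event-free to Day 7, in line with the in-hospital primary endpoint. If the intended event is adjudicated ARF, reconcile this sentence with the primary endpoint in section C openly; the substitution should not be made silently.

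The cost is a change of SAP wording. The overall survival analysis already needs dates of death, and the existing definition already needs dates of PPC, so no patients or visits are added.

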- Identification of factors associated with failure of prophylactic NIV in the subgroup where NIV was prematurely discontinued.

Statistical Justification for Sample Size:

Previously described data indicate that the expected effect size is approximately a 50% reduction in events:

- In studies on medical populations, the effect of prophylactic NIV was observed even on harder endpoints than ours: -66% reduction in reintubation, -51% reduction in ARF incidence, and -50% reduction in reintubations, and again -69% reduction in ARF incidence.

- In surgical populations, prophylactic NIV has led to a reduction in restrictive syndrome of about 50%, an improvement in pulmonary function tests (PFTs) of +30%, and a decrease in length of stay by 7 days.
- In curative use after abdominal surgery—a more unfavorable situation since ARF is more advanced—Squadrone reported favorable outcomes in 90% of cases with CPAP, and reintubations were reduced by 30%.

Given that the expected incidence of ARF in the high-risk group is 30–50%, a sample size of at least 121 subjects per arm is required to demonstrate, under a two-sided hypothesis, a relative reduction of 50% in ARF between a group managed with prophylactic NIV (15%) and a group managed with standard care (30%), with an alpha risk of 5% and a beta power of 90%. We anticipate 10% of patients will be non-evaluable.

The required sample size is therefore $242 + 24 = 266$ high-risk subjects evaluated for PPC.

STATISTICAL STOPPING RULES:

No interim analysis is planned in the protocol. However, if during the review of safety and efficacy data provided to the independent monitoring committee (raw, descriptive, and summarized data without pre-established statistics by the investigator or sponsor), a highly significant difference is identified for the primary endpoint or one of the safety parameters when comparing the two groups blinded to treatment allocation, the committee may decide to stop the study.

METHOD FOR HANDLING MISSING, UNUSED, OR INVALID DATA:

Patients included in the study for whom an endpoint is not available will not be considered in the analysis for that missing endpoint. No imputation method will be used for missing data.

MANAGEMENT OF CHANGES TO THE INITIAL ANALYSIS PLAN:

Modifications to the initial analysis plan may be proposed by the monitoring committee (interim analysis, statistical tests, adverse events, secondary objectives) if new literature data justify them.

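### Two exploratory NIV analyses use groups formed by events after randomisation, so as written they yield a biased contrast and an uninformative or selected association

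*Combined protocol and SAP*

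**What the plan says.** Section E of the combined protocol and SAP, under Subgroup Analyses (Exploratory), opens its list with "Subgroup analyses will address the occurrence of endpoints". Two of the three items matter here.

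- Analysis 1: "The subgroup of patients receiving NIV as curative (under conditions noted at session start) will be compared to the group receiving NIV only prophylactically", and the comparison is "in terms of outcome at Day 7".
- Analysis 2: "Identification of factors associated with failure of prophylactic NIV in the subgroup where NIV was prematurely discontinued".

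Curative NIV is not defined beyond the reference to conditions recorded when a session starts. Failure is not defined, and the Day 7 outcome is not named. The text does not say whether control-arm patients who receive curative NIV enter analysis 1. It names no comparison group for analysis 2, and neither item mentions timing or indication for treatment.

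Other parts of the document bear on the reading:

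- The primary endpoint in Section C is "Occurrence of acute respiratory failure (ARF) within 7 postoperative days during hospitalization".
- The sample-size justification contrasts prophylactic use with another setting: "In curative use after abdominal surgery—a more unfavorable situation since ARF is more advanced". This suggests that curative NIV means NIV given once ARF is present.
- The secondary endpoints count NIV days "including prophylactic and therapeutic NIV", and define intolerance through sessions ended early.
- Study of Associations sets two-sided tests at 0.05 and a relative risk with 95% CI for each presumed risk factor.

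**The concern.** A patient moves from prophylactic-only to curative NIV by deteriorating. A patient enters the discontinued subgroup because treatment stopped. Both events follow randomisation and are tied to endpoints, so randomisation protects neither analysis.

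In analysis 1, group membership is largely a marker of having become ill. A difference at Day 7 would then say little about what curative NIV does, yet the general testing rule could attach a very small p-value to it. In analysis 2, restricting the population to discontinued patients either removes the non-failures needed for a comparison or conditions on an event that itself needs explaining. The likely result is a misleading contrast in one analysis and an uninformative or selected association in the other.

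**Working it through.** The plan gives no figure for either analysis. Its only design figure is 121 per arm, used here solely as a denominator. The standard two-sided formula for 30% versus 15% gives 121 at 80% power and 161 at the stated 90%. That is a separate matter, and nothing below depends on it.

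**Analysis 1, outcome ARF**

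Inputs from the plan: N = 121 in the NIV arm; ARF 15% with prophylactic NIV and 30% with standard care. Inputs assumed, because the plan does not give them: q, the share of ARF patients given curative NIV (50–100%), and f, the share of patients without ARF given it (0–5%).

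Formulas, with A = 0.15 × 121 = 18.15 ARF patients and B = 121 − 18.15 = 102.85 others:

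- curative group: size qA + fB; ARF proportion qA / (qA + fB)
- prophylactic-only group: size 121 − (qA + fB); ARF proportion (1 − q)A divided by that size

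| q | f | Curative: n, ARF | Prophylactic-only: n, ARF | Risk ratio |
|---|---|---|---|---|
| 100% | 0% | 18, 100% | 103, 0% | undefined |
| 100% | 5% | 23, 78% | 98, 0% | undefined |
| 80% | 0% | 15, 100% | 106, 3.4% | 29 |
| 80% | 5% | 20, 74% | 101, 3.6% | 21 |
| 50% | 0% | 9, 100% | 112, 8.1% | 12 |
| 50% | 5% | 14, 64% | 107, 8.5% | 7.5 |

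Last row in full: 9.075 / (9.075 + 5.14) = 64%; 9.075 / 106.8 = 8.5%; 0.638 / 0.085 = 7.5. No effect of curative NIV enters any row.

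If control-arm patients given curative NIV are added (30% ARF, same q and f), the curative group grows to 27–64 patients with 74–100% ARF, against the same 0–8.5%. The comparison then also mixes the randomised arms.

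**Analysis 1, other outcomes**

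For death, reintubation or ventilation days, status at session start precedes the outcome, so the contrast is not circular in the same sense. Three problems remain.

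- Curative patients have a worse prognosis because of the indication.
- They must survive, still in hospital, until the indication arises, which is immortal time in their favour. The net direction of bias is therefore not fixed.
- A patient who deteriorates and is reintubated without a curative session stays in the prophylactic-only group.

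For NIV days, therapeutic NIV also counts in the endpoint itself.

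**Analysis 2**

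*Failure means premature discontinuation.* Let a discontinued patients have a given factor and b lack it. The risk of failure is a/a = 1 and b/b = 1. The relative risk equals 1 by identity whatever the factor, and the odds ratio is (a × 0) / (b × 0), which is undefined. No association can be estimated.

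*Failure means later ARF or reintubation.* Discontinued patients without that event form a comparator, and an estimate exists. It applies only to patients selected by a post-randomisation event, and a factor that influences stopping can appear associated with failure, or lose its association, through that selection.

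**The case against.** The strongest reply is that the text leaves room for milder readings. Curative NIV and the Day 7 outcome are undefined, so strict circularity needs two assumptions: that curative means given for ARF, and that the outcome is ARF. The first is a fair inference from the sample-size text. The second is only one of several endpoints that the list could cover. Likewise, the absence of a comparator in analysis 2 follows only if failure means discontinuation. The line could even be a loose way of asking what distinguishes discontinued patients from the rest. Premature discontinuation is a treatment-delivery event that overlaps with the intolerance endpoint, not with the primary one. Both analyses are labelled exploratory and feed neither the primary comparison nor the sample size. The authors themselves call curative use the less favourable situation, so they know of the prognostic imbalance.

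Most of this stands as a limit on the wording. A reader might infer that analysis 1 is circular for every outcome, that analysis 2 can never produce an estimate, or that one figure such as a risk ratio of 29 measures the bias. The documents support none of these. The first two depend on undefined terms, and 29 is one row of an assumed range.

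The reply does not rescue the analyses. Each milder reading replaces circularity or inestimability with confounding by indication, immortal time or selection after randomisation, and the plan handles none of them. An exploratory label warns about multiplicity and chance; it does not remove a bias built into the grouping.

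**Conclusion.** The point holds in conditional form, as a minor one. Both analyses rest on groups formed by post-randomisation events.

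- Analysis 1 is circular if curative means given for ARF and the outcome is ARF. Under the assumed shares above, the risk ratio is then about 7.5 or more with no effect of curative NIV. For death, reintubation or ventilation days it is confounded by indication and subject to immortal time, and no size can be given from the documents.
- Analysis 2 yields no association if failure means discontinuation, and a selected one if it means later ARF or reintubation.

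A reader might go further and infer that the trial's main result is compromised, or that such a contrast would show harm from curative NIV. Neither is supported. The intention-to-treat comparison of randomised arms does not use these groups, and the illustration produces the contrast without any treatment effect.

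**What to change.** 1. State in the SAP the definitions of curative NIV and of failure used in the analysis, and say which arms contribute to analysis 1.
2. Replace analysis 1 with a description of Day 7 outcomes in curative-NIV patients, by randomised arm, with no between-group test. Leave inference to the randomised comparisons. A comparison by arm of how many patients received curative NIV (relative risk, 95% CI) may be added as supportive, noting that in an open-label trial it depends on clinician judgement.
3. Run the failure-factor analysis in all NIV-arm patients who started prophylactic NIV, with premature discontinuation (yes/no) as the outcome and baseline factors as predictors.

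The cost is SAP rewording and the loss of a formal p-value for analysis 1. The data are essentially those already planned, since conditions at session start and NIV days are to be recorded. The primary analysis and sample size do not change.

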Statistical analyses will be performed using R software and IBM SPSS.

A total of 266 patients are planned for inclusion, divided into two balanced groups.

DESCRIPTION OF PLANNED STATISTICAL METHODS:

Research Protocol

Patients will be analyzed on an intention-to-treat basis and then per-protocol.

Intention-to-treat analysis: all patients included in the study for whom outcome data are available will be considered in the analysis according to their randomization group. No imputation method will be used in case of missing data.

If organizational constraints prevent the patient from receiving prophylactic NIV (despite inclusion in the corresponding intervention arm), the patient will remain in their randomization arm for the entire study duration, and their data will be analyzed on an intention-to-treat basis.

Per-protocol analysis excludes patients for whom the initial protocol was not fully adhered to. Only patients who followed the protocol will be considered in the analyses, within the arm to which they were originally randomized.

The analysis will focus on the primary endpoint to determine whether randomization to the "PPC prevention strategy" arm leads to a reduction in PPC frequency compared to the control group. Effect size and number needed to treat will be calculated.

Similarly, for secondary endpoints, significant differences between the two groups will be sought in terms of:

- a) Safety and tolerability of the strategy under study (see safety assessment parameters)
- b) Mortality during hospitalization
- c) Patient reintubation
- d) Length of stay and duration of invasive or non-invasive mechanical ventilation

Description of the overall analysis method

The significance threshold is set at 0.05, and all tests will be two-sided. For qualitative variables, results will be reported as counts and percentages. For quantitative variables, results will be reported as means and standard deviations in case of normal distribution, and as medians with 25th and 75th percentiles in the absence of a Gaussian distribution. Normality of continuous variables will be assessed using the Kolmogorov-Smirnov test.

A simple descriptive analysis will be performed on the entire study population and by subgroups. This description will include sociodemographic data, medical history, ongoing treatments, etc.

A qualitative and quantitative analysis of missing data will be performed. No imputation of missing data is planned for the endpoints.

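### The 121 patients per arm give about 80% power at the plan's own rates (30% versus 15%), not the stated 90%, so the type II error is about twice what is declared.

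*Combined protocol and SAP*

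**What the plan says.** Section E, under the statistical justification for sample size, states that "a sample size of at least 121 subjects per arm is required to demonstrate, under a two-sided hypothesis, a relative reduction of 50% in ARF". The two rates follow: "a group managed with prophylactic NIV (15" per cent) and "a group managed with standard care (30" per cent). The error rates are given as "with an alpha risk of 5% and a beta power of 90" per cent. The plan then expects 10% of patients to be non-evaluable and concludes: "The required sample size is therefore $242 + 24 = 266$ high-risk subjects evaluated for PPC".

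The rest of section E is consistent with these inputs. The overall analysis method says "The significance threshold is set at 0.05, and all tests will be two-sided", allocation is 1:1, and the total of 266 is repeated. Binary variables are to be compared by Pearson's chi-square, with Fisher's exact test as the alternative. The documents nowhere mention 80% power and give no other derivation.

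**The concern.** The number 121 is the familiar answer for 30% versus 15% at 80% power, so its pairing with 90% suggested that either the power or the sample size was misstated.

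This is the plan's only power statement for its primary endpoint. Anyone judging whether the trial is large enough, or reading a non-significant result, will rely on it. If the type II error is 20% rather than 10%, a negative result is weaker evidence against a halving of ARF than the plan implies, and could be over-read.

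**Working it through.** **Inputs, all from section E.** Control rate p1 = 0.30; NIV rate p2 = 0.15; two-sided alpha 0.05 (z = 1.960); 1:1 allocation; stated power 90% (z = 1.2816); 121 evaluable per arm; 10% non-evaluable; 266 in total. For 80% power, z = 0.8416.

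**Formula (pooled variance under the null).** With mean rate p = (0.30 + 0.15)/2 = 0.225,

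n per arm = [1.960·√(2p(1−p)) + z_power·√(p1(1−p1) + p2(1−p2))]² / (p1−p2)²

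- √(2 × 0.225 × 0.775) = 0.5906, and 1.960 × 0.5906 = 1.1575
- √(0.30 × 0.70 + 0.15 × 0.85) = √0.3375 = 0.5809
- (p1−p2)² = 0.0225

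**Reproducing the plan's figure.**

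- 80% power: (1.1575 + 0.8416 × 0.5809)² / 0.0225 = (1.1575 + 0.4889)² / 0.0225 = 120.5, rounded up to **121**, the plan's number.
- 90% power: (1.1575 + 1.2816 × 0.5809)² / 0.0225 = (1.1575 + 0.7445)² / 0.0225 = 160.8, rounded up to **161**.

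**Other standard methods.** None gives 121 at 90% power.

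| Method | n per arm, 80% | n per arm, 90% |
|---|---|---|
| Pooled, two-sided | 121 | 161 |
| Unpooled, two-sided | 118 | 158 |
| Arcsine, two-sided | 119 | 159 |
| Continuity-corrected, two-sided | 134 | 174 |
| Pooled, one-sided 5% (excluded by the plan) | 95 | 131 |

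**Power delivered.** For the normal approximation, z_power = [0.15·√n − 1.1575] / 0.5809.

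- n = 121: (1.6500 − 1.1575) / 0.5809 = 0.848, so power is 80.2% and the type II error 19.8%. Against the declared 10%, the ratio is 19.8/10, about 2.0.
- n = 133: power is 83.8%.

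| Evaluable per arm | Normal approximation | Exact, Pearson | Exact, Fisher |
|---|---|---|---|
| 121 | 80.2% | 80.9% | 76.4% |
| 133 (266/2, no losses) | 83.8% | 84.4% | 80.8% |

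**What would give 90% at 121 per arm.** Either an NIV rate of 13.0% against 30% (relative risk 0.130/0.30 = 0.43), or a control rate of about 37% with the relative risk kept at 0.50.

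**Side check on the allowance.** The plan adds 10% (242 + 24 = 266). Allowing for a 10% loss means dividing: 242/0.9 = 268.9, so 269. With 266 randomised, 266 × 0.9 = 239.4 are evaluable, or 119.7 per arm, and power is 79.7%. The effect is about half a percentage point.

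**The case against.** The best defence is that the plan sizes at the bottom of its own expected range. It expects an ARF incidence of 30–50% in this population. With the same 50% relative reduction, 121 per arm gives 87.6% power at a control rate of 35%, 90.0% at 37%, 92.9% at 40% and 98.3% at 50%. The trial may therefore have 90% power or more if ARF is commoner than 30%. That is true, and it means the 20% type II error must be quoted as conditional on 30% versus 15%. It does not rescue the sentence, because the plan attaches the 90% to exactly those two rates.

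A second objection is that the expression "a beta power of 90" per cent is loose and may be a translation slip. Neither reading helps: 121 per arm fits neither a power of 90% nor a beta of 90%.

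Third, the match at 80% makes a misstated power the likely explanation but does not prove what the sponsor intended. This stands, and the sponsor should confirm which figure was meant.

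Fourth, the Fisher figure should not be given much weight. The plan names Pearson's chi-square first, and with about 18 and 36 expected events (121 × 0.15 and 121 × 0.30) the usual small-count reason for Fisher's test would not arise. That is fair. The allowance and the choice of test are side notes, and the finding does not depend on them.

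Finally, the planned relative risk with its 95% confidence interval is a better guide to a negative result than the design power. That softens the consequence but does not make the stated power correct.

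**Conclusion.** The concern holds. The stated sample size and the stated power cannot both be right. This rests only on inputs printed in the plan (30% versus 15%, two-sided 5%, 1:1, 121 evaluable per arm) and on an unadjusted comparison of two proportions. The shortfall is about 10 percentage points of power or, viewed the other way, 40 evaluable patients per arm (161 − 121). Full retention recovers less than half of the missing power. The error is in a declared operating characteristic of the primary analysis and should be corrected before results are known.

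**What to change.** Restate the power as about 80%, with its conditions: ARF 30% versus 15%, two-sided 5%, 121 evaluable per arm, uncorrected Pearson chi-square. Replace the term used for power with plain wording. This costs one sentence and no patients or data; the declared power simply becomes less favourable.

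If the sponsor did intend 90%, the sample size has to change instead: 161 evaluable per arm, 322 in total, and 322/0.9 = 357.8, so 358 randomised. That is 92 more than the 266 planned.

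Two small points can go into the same edit. Either correct the allowance to 242/0.9 = 269, or say that 266 randomised leaves about 239 evaluable. Also name the uncorrected Pearson chi-square as the test for the primary endpoint, so that the power statement and the analysis refer to the same test. It would also help to tabulate power across the plan's expected control range, since that is where 90% could legitimately appear.
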